For nodule size, grip strength, range of motion of the affected digit, Michigan Hand Outcomes Questionnaire, patient identified activity most restricted by DD, progression to surgery, and injection experience linear mixed effects regression models will be used. This procedure will allow for data from all follow-up time-points to be accounted for, and for adjustment for baseline measures to be made, where applicable. The time (days) between baseline injection and each follow-up time-point will be included in the models as a random effect to account for patients not all having their follow-up assessments at the same time.

Repurposing anti-TNF for treating Dupuytren's disease (funded by Health Innovation Challenge Fund, Wellcome Trust)  
EudraCT Number: 2015-001780-40 and OCTRU Reference Number CTU0028

As per the primary outcome, initial analyses for all secondary outcomes will be unadjusted and additional adjusted analyses will be carried out further accounting for centre (Oxford, Edinburgh or Groningen) and age (as a continuous variable) and baseline if appropriate. For all models, assessments for interaction between time since baseline treatment and baseline measurement will be carried out to assess if any effect of baseline measurement changes over time.

For all secondary outcome analyses, mean difference and associated 95% confidence intervals will be reported. If severe departures from normality are identified in secondary outcome measurements, the data will be log-transformed in order to gain normality and geometric means with 95% confidence intervals will be reported. If the data are not normally distributed – or near normally distributed – after log transformation, the non-parametric Mann-Whitney test will be used with no adjustment for baseline, and the median change with 95% confidence intervals will be reported.

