Patient identified activity most restricted by DD: Participants will be asked at baseline to identify the activity most restricted by DD and to rate the restriction on a scale of 1-10. At secondary co-time points (3, 6, 9, 12, and 18 months), participants will be asked to again rate the restriction of the same activity. When applied to DD, significant improvement in median scores have been reported following fasciectomy (Engstrand, Boren and Liedberg, 2009).

Progression to surgery: Only for the digit being treated at the end of follow-up (18 months post-first injection).

Injection experience: Reported by patients using an injection questionnaire which incorporates a Visual Analogue Scale of 0 (no pain) to 10 (extreme pain). Injection experience is measured after each research injection, at baseline, 3, 6 and 9 months.

Repurposing anti-TNF for treating Dupuytren's disease (funded by Health Innovation Challenge Fund, Wellcome Trust)

EudraCT Number: 2015-001780-40 and OCTRU Reference Number CTU0028

**Adverse events (injection site assessment):** The most common adverse reaction with adalimumab is injection site reactions. The injection site will be monitored for adverse events using an 'Injection Site Response Form'; the injection responses are based on injection site reactions in the prescribing literature and in clinical trials.

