### **6.3 Analysis methods: Secondary outcomes**

The secondary analyses will be performed on the ITT population, comparing intervention (adalimumab) against placebo (saline, 0.9% NaCl) for all randomised participants with available data.

Mixed effects regression models will be used to analyse secondary outcomes data, with linear regression for continuous variables and logistic regression for binary variables. Mixed effects regression allows for data from all follow-up time-points to be accounted for, and for adjustment for stratification factors and baseline measurements to be made, where applicable. This procedure is robust and is able to deal with some missing values, either due to missed visits or patients leaving the study prematurely. The time (days) between baseline injection and each follow-up time-point will be included in the models as a random effect to account for patients not all having their follow-up assessments at the same time.

As per the primary outcome, initial analyses for all secondary outcomes will be unadjusted. These analyses will include only outcome measurement and treatment arm, with time since first injection included as a random effect and baseline outcome measurement as a fixed effect. Additional adjusted analyses will be carried out further accounting for centre (Oxford, Edinburgh or Groningen) and age (as a continuous variable). For all models, where appropriate, treatment by time interaction terms will be incorporated to account for changes in effects between treatment arms over follow-up.

Repurposing anti-TNF for treating Dupuytren's disease (funded by Health Innovation Challenge Fund, Wellcome Trust)  
EudraCT Number: 2015-001780-40 and OCTRU Reference Number CTU0028

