For progression to surgery – a binary secondary outcome – numbers and proportions will be reported with absolute odds (odds difference) and relative odds (odds ratio), and associated 95% confidence intervals. For all continuous secondary outcomes, mean difference and associated 95% confidence intervals will be reported. For continuous measures if severe departures from normality are identified in secondary outcome measurements, the data will be log-transformed in order to gain normality and geometric means with 95% confidence intervals will be reported. If the data are not normally distributed – or near normally distributed – after log transformation, the non-parametric Mann-Whitney test will be used with no adjustment for baseline, and the median difference with 95% confidence intervals will be reported.

**Appendix 5: Outcome measure summaries, Table 10a:** Mean (with SD) nodule size, as maximal nodule feret and maximal height, recorded at each study time-point.

**Appendix 5: Outcome measure summaries, Table 10b:** Mean (with SD) nodule area recorded at each study time-point.

**Appendix 5: Outcome measure summaries, Table 11:** Mean (with SD) grip strength recorded at each study time-point.

**Appendix 5: Outcome measure summaries, Table 12a:** Mean (with SD) affected digit range of motion active measurements recorded at each study time-point.

**Appendix 5: Outcome measure summaries, Table 12b:** Mean (with SD) affected digit range of motion passive measurements recorded at each study time-point.

**Appendix 5: Outcome measure summaries, Table 13a:** Mean (with SD) Michigan Hand Outcomes Questionnaire overall score recorded at each study time-point.

**Appendix 5: Outcome measure summaries, Table 13b:** Mean (with SD) Michigan Hand Outcomes Questionnaire individual component scores recorded at each study time-point.

**Appendix 5: Outcome measure summaries, Table 14:** Mean (with SD) score for most restricted activity recorded at each study time-point.

**Appendix 5: Outcome measure summaries, Table 15:** Mean (with SD) injection experience pain score recorded at each study time-point.

**Appendix 5: Outcome measure summaries, Table 16:** Frequency and percentage of participants progressing to surgery at each study time-point

**Appendix 5: Outcome measures analysis, Table 18a:** Maximal nodule feret mixed-effects regression results for all follow-up time-points.

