**Appendix 5: Outcome measures analysis, Table 18b:** Maximal nodule height mixed-effects regression results for all follow-up time-points.

**Appendix 5: Outcome measures analysis, Table 19:** Grip strength mixed-effects regression results for all follow-up time-points.

**Appendix 5: Outcome measures analysis, Table 20a:** Affected digit range of motion active measurements mixed-effects regression results for all follow-up time-points.

**Appendix 5: Outcome measures analysis, Table 20b:** Affected digit range of motion passive measurements mixed-effects regression results for all follow-up time-points.

**Appendix 5: Outcome measures analysis, Table 21:** Michigan Hand Outcomes Questionnaire mixed-effects regression results for all follow-up time-points.

Repurposing anti-TNF for treating Dupuytren's disease (funded by Health Innovation Challenge Fund, Wellcome Trust)

EudraCT Number: 2015-001780-40 and OCTRU Reference Number CTU0028

**Appendix 5: Outcome measures analysis, Table 22:** Injection experience pain score mixed-effects regression results for all follow-up time-points.

**Appendix 5: Outcome measures analysis, Table 23a:** Absolute odds of progression to surgery, from mixed-effects regression results for all follow-up time-points.

**Appendix 5: Outcome measures analysis, Table 23b:** Relative odds of progression to surgery, from mixed-effects regression results for all follow-up time-points.

**Appendix 5: Outcome measures analysis, Table 24:** Most restricted activity mixed-effects regression results for all follow-up time-points

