Work performance									

Repurposing anti-TNF for treating Dupuytren's disease (funded by Health Innovation Challenge Fund, Wellcome Trust)  
EudraCT Number: 2015-001780-40 and OCTRU Reference Number CTU0028

	Saline			Adalimumab			Total			
	N =	n	Mean	SD	n	Mean	SD	n	Mean	SD
Baseline										
3 month										
6 month										
9 month										
12 month										
18 month										
Pain										
Baseline										
3 month										
6 month										
9 month										
12 month										
18 month										
Aesthetics										
Baseline										
3 month										
6 month										
9 month										
12 month										
18 month										
Patient satisfaction with hand function										
Baseline										
3 month										
6 month										

Repurposing anti-TNF for treating Dupuytren's disease (funded by Health Innovation Challenge Fund, Wellcome Trust)  
EudraCT Number: 2015-001780-40 and OCTRU Reference Number CTU0028

	Saline N =			Adalimumab N =			Total N =		
	n	Mean	SD	n	Mean	SD	n	Mean	SD
9 month									
12 month									
18 month									

**Table 16:** Mean (with SD) score for most restricted activity recorded at each study time-point

	Saline N =			Adalimumab N =			Total N =		
	n	Mean	SD	n	Mean	SD	n	Mean	SD
Baseline									
3 month									
6 month									
9 month									
12 month									
18 month									

**Table 17:** Mean (with SD) injection experience pain score recorded at each study time-point

	Saline N =			Adalimumab N =			Total N =		
	n	Mean	SD	n	Mean	SD	n	Mean	SD
Baseline									
3 month									
6 month									
9 month									
12 month									
18 month									

Repurposing anti-TNF for treating Dupuytren's disease (funded by Health Innovation Challenge Fund, Wellcome Trust)  
EudraCT Number: 2015-001780-40 and OCTRU Reference Number CTU0028

**Table 18:** Frequency and percentage of participants progressing to surgery at each study time-point

	Saline		Adalimumab		Total	
	N =	n	N =	n	N =	n
		%		%		%
Baseline						
3 month						
6 month						
9 month						
12 month						
18 month						

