**(iii) PIP – extension with MCP flexed**

	Saline			Adalimumab			Treatment effect		
	N =			N =			N =		
	n	Mean change	SD	n	Mean change	SD	Mean difference	95% confidence interval	P-value
Unadjusted a									
12 months									
Adjusted b									
Baseline									
3 months									
6 months									
9 months									
12 months c									
18 months									

a passive PIP extension with MCP flexed of affected digit and treatment arm | b passive PIP extension with MCP flexed of affected digit, treatment arm, age group and centre | c primary endpoint

Repurposing anti-TNF for treating Dupuytren's disease (funded by Health Innovation Challenge Fund, Wellcome Trust)  
EudraCT Number: 2015-001780-40 and OCTRU Reference Number CTU0028

**Table 23:** Michigan Hand Outcomes Questionnaire mixed-effects regression results for all follow-up time-points

	Saline N =			Adalimumab N =			Treatment effect N =		
	n	Mean change	SD	n	Mean change	SD	Mean difference	95% confidence interval	P- value
Unadjusted a									
12 months									
Adjusted b									
Baseline									
3 months									
6 months									
9 months									
12 months c									
18 months									

a MHQ and treatment arm | b MHQ, treatment arm, age group and centre | c primary endpoint

**Table 24:** Injection experience pain score mixed-effects regression results for all follow-up time-points

	Saline N =			Adalimumab N =			Treatment effect N =		
	n	Mean change	SD	n	Mean change	SD	Mean difference	95% confidence interval	P- value
Unadjusted a									
Baseline									
3 months									
6 months									
9 months									
Adjusted b									

Repurposing anti-TNF for treating Dupuytren's disease (funded by Health Innovation Challenge Fund, Wellcome Trust)  
EudraCT Number: 2015-001780-40 and OCTRU Reference Number CTU0028

	Saline N =			Adalimumab N =			Treatment effect N =		
	n	Mean change	SD	n	Mean change	SD	Mean difference	95% confidence interval	P-value
Baseline									
3 months									
6 months									
9 months									

a injection experience and treatment arm | b injection experience, treatment arm, age group and centre

**Table 25a:** Absolute odds of progression to surgery, from mixed-effects regression results for whole study period

	Saline N =		Adalimumab N =		Total N =		

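### Progression to surgery is one binary result per person at 18 months, yet the plan assigns it to mixed models and reports an odds difference where a risk difference is needed

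*SAP*

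**What the plan says.** - **Outcome.** SAP 6.1 defines progression to surgery thus: "Only for the digit being treated at the end of follow-up (18 months post-first injection". SAP 6.3 calls it binary. SAP Tables 1 and 2 mark it at 18 months alone, and the Part 2 objectives table in Protocol 5 gives the same time.
- **Model, outline text.** The list of outcomes in SAP 3.7 ends: "progression to surgery, and injection experience linear mixed effects regression models will be used". Protocol 11.2 carries the same sentence.
- **Model, detailed text.** SAP 6.3 uses mixed effects regression, "with linear regression for continuous variables and logistic regression for binary variables". The initial secondary analyses "will include only outcome measurement and treatment arm, with time since first injection included as a random effect", and the baseline value as a fixed effect.
- **Effect measures.** For surgery, "numbers and proportions will be reported with absolute odds (odds difference) and relative odds (odds ratio", with 95% intervals. No risk difference is planned.
- **Tables.** The list in SAP 6.3 has "Absolute odds of progression to surgery, from mixed-effects regression results for all follow-up time-points". The matching shell, Table 25a of Appendix 5, is titled "Absolute odds of progression to surgery, from mixed-effects regression results for whole study period" and has 18-month rows only, as does the odds-ratio shell that follows it. A separate descriptive shell gives "Frequency and percentage of participants progressing to surgery at each study time-point".

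**The concern.** The outline and detailed sections name different models for surgery, and both are mixed models for repeated records. The definition and the model shells give one result per person, so there is no within-person information for a random effect to describe.

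The second issue is the scale. An odds difference is hard to interpret, and a reader can easily take it for a difference in the percentage having surgery. Surgery is among the outcomes that matter most to patients in this trial, so the absolute effect should be on a scale that can be read directly and should carry its own interval.

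A smaller point concerns the repeated secondary outcomes. Time in days is the only random effect that SAP 3.7, SAP 6.3 and Protocol 11.2 name, and no participant term or within-person covariance is stated.

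**Working it through.** **1. Which model does one record per person support?** A linear mixed model gives differences in means or proportions. It cannot give the odds ratio or odds difference that SAP 6.3 and the shells ask for, so the linear listing does not fit the SAP's own outputs. In a mixed logistic model, one binary value per person cannot identify a participant variance. Assumed rates of 20% and 10% are fitted equally well by these conditional odds ratios, depending on the random-effect SD that is supposed:

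| Random-effect SD | Conditional odds ratio |
|---|---|
| 0 | 0.444 |
| 1 | 0.401 |
| 2 | 0.305 |
| 3 | 0.214 |

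Only the first is the ordinary odds ratio: (0.10/0.90)/(0.20/0.80) = 0.111/0.250 = 0.444.

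**2. Odds difference against risk difference.** With p1 for adalimumab and p2 for saline, the risk difference is p1 - p2 and the odds difference is p1/(1-p1) - p2/(1-p2). The rates are assumptions.

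| p1 v p2 | Risk difference | Odds difference |
|---|---|---|
| 2% v 5% | -0.030 | 0.0204 - 0.0526 = -0.032 |
| 5% v 10% | -0.050 | 0.0526 - 0.1111 = -0.058 |
| 10% v 20% | -0.100 | 0.1111 - 0.2500 = -0.139 |
| 20% v 40% | -0.200 | 0.2500 - 0.6667 = -0.417 |

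**3. Intervals.** The number per arm comes from the plan's sample size (SAP 3.3), which reproduces: 2(1.960 + 1.282)²/0.62² = 54.7, so 55 per arm; 55/0.8 = 68.75, so 69 per arm and 138 in all. With 55 per arm, the variance of the risk difference is the sum of p(1-p)/n over the arms. The variance of the odds difference, by the delta method, is the sum of p/[n(1-p)³].

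- 10% v 20%: risk difference SE √(0.25/55) = 0.067, interval -0.23 to 0.03. Odds difference SE √(0.00249 + 0.00710) = 0.098, interval -0.33 to 0.05.
- 20% v 40%: risk difference SE √(0.40/55) = 0.085, interval -0.37 to -0.03. Odds difference SE √(0.00710 + 0.03367) = 0.202, interval -0.81 to -0.02.

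**4. Repeated secondary outcomes.** Type I error at a nominal 5%, with five visits, 110 people and assumed residual correlations of 0.3/0.5/0.7:

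- One pooled arm effect, no participant term: 2[1 - Φ(1.96/√(1+4r))] = 18.6/25.8/31.5%.
- Arm-by-visit contrasts, no participant term: 4.5% to 5.4% by simulation.
- Participant slope on days but no intercept, arm-by-visit contrasts: 4% to 5% at 12 months, about 8/11/15% at 3 months and 2/1/1% at 18 months.
- Participant random intercept: 4% to 6% throughout.
- Random intercept plus slope, pooled effect, r = 0.5: 5.3% (150 runs, Monte Carlo SE about 1.8%).

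**The case against.** **SAP 6.3 settles linear against logistic.** Protocol 11 leaves full details to the SAP, SAP 3.7 is an outline that largely repeats the protocol, and 6.3 calls surgery binary and plans an odds ratio. This stands: logistic is intended and the linear listing is left-over text. It does not rescue the mixed model or the odds difference, both of which 6.3 keeps.

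**Surgery is recorded more than once.** Protocol 4 has it recorded throughout the 18 months. Appendix 6 of the SAP includes it in the posted questionnaires, which were repeated at delayed visits. Item (iv) of 15.1 would add repeat questionnaires as a further time-point, and surgery is on the list of Covid sensitivity analyses in Appendix 5. This also stands, and the fix has to deal with it. The analysed outcome is still status at 18 months, and the by-visit table is descriptive.

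**The odds difference does little harm.** Proportions per arm and an odds ratio with an interval are already planned, and up to 10% the two scales differ by less than 0.01. In both worked cases the two intervals agree on whether zero is excluded. That is fair: the issue is how the effect is read, not a false test result.

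**A stronger reading that the documents do not support.** Because time is the only named random effect, a reader might infer that the repeated secondary analyses ignore within-person correlation and have type I error of 19% to 31%. SAP 1.2 speaks of repeated measures, SAP 6.2 of multilevel models, and SAP 6.3.2 of a model still called mixed once random time is removed. All three presuppose a participant term. Those error rates apply only to a pooled effect fitted without one; by-visit contrasts, which most shells imply, stay near 5% even then.

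**Conclusion.** The surgery point holds. A binary outcome with one 18-month result per person is assigned to a linear mixed model in two places and, by implication, to a mixed logistic model in a third; neither suits it. Its only planned absolute between-arm effect is an odds difference. That overstates the difference in risk by about 40% at 10% v 20% (0.139/0.100), roughly doubles it at 20% v 40% (0.417/0.200), and barely differs when surgery is rare. These sizes rest on assumed rates.

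For the repeated secondary outcomes, the omission of a named participant effect is missing detail and not an error. The primary ANCOVA and the sample size are untouched, and SAP 4.1 treats secondary outcomes as supportive only.

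**What to change.** For surgery:

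- Analyse status by 18 months with ordinary single-level logistic regression, unadjusted and then adjusted for centre and age.
- Report a risk difference and an odds ratio, each with a 95% interval, in place of the odds difference.
- Delete surgery from the linear mixed model lists in SAP 3.7 and Protocol 11.2, and exempt it from the mixed-model wording in SAP 6.3 and 6.3.2.
- Align the table titles listed in SAP 6.3 with the 18-month shells in Appendix 5.
- In the Covid sensitivity analyses (SAP 15.1), use a repeat-questionnaire report of surgery to update the 18-month status under item (iii), not as an extra time-point under item (iv).

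As a clarification for the repeated-measures secondary outcomes, name a participant random intercept. Keep time in days as a fixed effect, with a random slope added to the intercept, so that actual assessment dates are still used. When SAP 6.3.2 removes random time, retain the intercept; the sensitivity model then differs from the main one only in the random slope.

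The cost is wording changes in the SAP, Protocol 11.2 and the table shells. No new data are needed.

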#### 6.3.1 Missing data

The number and proportion of individuals in the missing category for each secondary outcome variable will be reported, as well as reasons for missing if known.

Missing data distributions will be explored to assess whether the assumption that data are missing at random (MAR) is true. For patient-reported outcomes, participants for whom full questionnaires have not been completed will be excluded from the analysis of the corresponding outcome. For partially completed patient-reported outcomes, missing values will be imputed according to scoring guidelines for the relevant PROM (see **Appendix 3**).

During the analysis, techniques other than those suggested above may be used, for instance if data are not normally distributed or in the case of new techniques being developed in the meantime. No data will be considered spurious in the analysis since all data will be checked and cleaned before analysis.

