## **Part 2. Randomised controlled trial**

For the randomised controlled part of the trial, participants will be recruited with **early DD** to assess the efficacy of injections of adalimumab in controlling disease progression including nodule hardness.

A maximum of 200 participants will be randomised to participate in the study if they meet the inclusion/exclusion criteria and provide written consent. We will select participants with early disease nodules who also give a clear history of activation and progression of the disease in the previous 3-6 months. Only participants with flexion deformities of  $\leq 30^\circ$  at the metacarpophalangeal and/or at the proximal interphalangeal joint of their fingers will be recruited, with a maximum total flexion deformity of  $60^\circ$ . All participants will be screened for TB, Hepatitis B and C and HIV. If results are positive for any test, the participant will not be eligible to enter the trial and will be informed and counseled about the result of their test. The participants will be randomised (1:1) to receive injections of either adalimumab or saline (placebo) into the active nodule. The dose will be an injection into the nodule of 40 mg adalimumab, or the equivalent volume of saline. The adalimumab formulation of 40 mg in 0.4 ml formulation will be used. The adalimumab or placebo will be administered at 3 monthly intervals for the first year i.e. each participant will be injected on 4 occasions over a 9 month period (baseline, 3, 6 and 9 months) and followed-up for a further 9 months. If, on a returning visit, the nodule has reduced in size to such an extent that the clinician is not satisfied they can accurately deliver a repeat injection, then the clinician may decide to not inject on that visit. In this event, the participant will be invited to all further visits as originally planned, and future planned injections may be given if the nodule recurs.

Study participants will be seen at 6 time points after screening: week 0, 3 months, 6 months, 9 months, 12 months and 18 months according to the flow chart (Appendix B: Trial Flow Chart Part 2). The schedule, duration of each visit and visit window is detailed in the Schedule of procedures (Appendix C: Schedule of procedures Part 2). Study participants will be contacted by telephone by a member of the research team at 1 week post baseline to monitor for Adverse Events.

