### 3.2 Randomisation and Blinding

Randomisation will be undertaken at or prior to the baseline visit prior to receiving the trial injection. Participants will be randomised 1:1 to placebo or adalimumab with stratification by age and centre. Participants will be randomised through a secure online service provided by the Oxford Clinical Trials Research Unit (OCTRUE) called RRAMP. RRAMP is used to randomise participants and this will generate a Trial ID and prompt an email to Pharmacy which informs them of which IMP (drug or placebo) to dispense.

Full details of the randomisation are available in **RIDD\_RBP\_v9.0\_18May2018**, stored in the confidential statistical section of the TMF.

The methods for blinding will be influenced by the packaging of the adalimumab being used. For part 2, pre-filled syringe is the only option for using the 40mg in 0.4ml formulation. Due to the distinctive appearance of the syringe, it is not possible to blind the healthcare professional administering the injection to treatment allocation. To protect the quality of the data, any person injecting with a pre-filled syringe will NOT be involved in administering any further trial procedures. Any healthcare professionals involved with administering any trial procedure, including outcome assessments, after the injection of IMP will be blinded to treatment.

The IMP (which will be stored in pharmacy) will be dispensed with accountability to a member of the research team who will take the IMP to a clinic room separate from the participant. Care will be taken to ensure any healthcare professionals blinded to treatment allocation are not present for the injection, and the syringe will be hidden from the participant's view.

In summary, participants and healthcare professionals involved in participant follow-up and outcome assessment will always be blinded to treatment allocation. Laboratory staff will be blinded to treatment allocation.

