### 3.3 Sample Size

The sample size is based on unpublished data acquired in a pilot study 'Ultrasonographic (grey scale) characteristics of DD and their relationship to the clinical features and functional severity of the disease: a pilot study' (REC Ref. 11/SC/0447). Within the study there were 25 participants with mean nodule hardness of  $53 \pm 8$  for participants suffering DD and  $32 \pm 3$  for corresponding controls matched by age and sex.

Using the study, a minimum of 138 participants (69 per arm) would be required to detect a moderate effect size of 0.62, based on a 5 point change in nodule hardness at 12 months and assuming a standard deviation of 8 (5% significance (2-sided) and 90% power, allowing for a 20% loss to follow up).

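### SAP 6.3.1 names the participant, not the visit, as the unit excluded when a questionnaire is wholly missing; read literally, this conflicts with the all-available-data mixed model in SAP 6.3

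*SAP*

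**What the plan says.** SAP 6.3.1 (Missing data, secondary outcomes) states that "participants for whom full questionnaires have not been completed will be excluded from the analysis of the corresponding outcome". The sentence after it deals with partly completed forms, whose missing items are imputed by the scoring guidelines in SAP Appendix 3. The exclusion therefore concerns wholly missing questionnaires. Neither sentence mentions a visit or time-point.

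SAP 6.3 analyses secondary outcomes in all randomised participants who have data, by mixed effects regression over all follow-up time-points. It describes this procedure as "able to deal with some missing values, either due to missed visits or patients leaving the study prematurely". Treatment arm and the baseline score enter as fixed effects. SAP 4.2 defines the intention-to-treat population by availability of outcome data.

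MHQ is scored at baseline, 3, 6, 9, 12 and 18 months (SAP 6.1). SAP 6.3.2 names it, with range of motion of the treated digit, as a key secondary outcome.

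**The concern.** The analysis of MHQ is a single model over all follow-ups, so excluding a participant from that analysis removes every visit, including completed ones. A programmer who follows the sentence as written would turn an all-available-data analysis into a completers analysis. That costs precision and selects participants on attendance, which may be related to disease progression or to arm.

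Two features of the plan make the wording matter more:

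- Multiple imputation and pattern-mixture modelling are specified for the primary outcome only (SAP 6.2.1). The sensitivity analyses for secondary outcomes (SAP 6.3.2 and Appendix 6) cover per-protocol, complier-average, timing, operated-digit and Covid-19 questions. None tests the effect of excluding people with missing forms.
- SAP 7 has an independent statistician repeat the key secondary analyses from this document. Two competent readers could build different MHQ datasets from it.

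The SAP's change log records a move from time-point ANCOVA to repeated-measures models for secondary outcomes. Excluding a participant does no harm when each visit is analysed separately, but it does in a joint model. The sentence may simply not have been adapted, though the documents do not say so.

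**Working it through.** **1. The plan's own figure.** SAP 3.3 states that "a minimum of 138 participants (69 per arm) would be required to detect a moderate effect size of 0.62". Its inputs are a difference of 5 points, an SD of 8, a two-sided alpha of 0.05, power of 90% and an allowance of 20% for loss. Allocation is 1:1 (SAP 3.2).

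- n per arm = 2(1.960 + 1.282)² / 0.62² = 54.7, rounded up to 55.
- Allowing for 20% loss: 55 / 0.8 = 68.75, rounded up to 69 per arm, or 138 in total.

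The figure reproduces. It concerns nodule hardness only; the documents give no power or missing rate for MHQ.

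**2. Literal rule, independent misses.** Let q be the chance that a questionnaire is wholly missing at a visit (assumed) and k the number of questionnaires: 5 follow-ups, or 6 with baseline. The share of participants excluded is 1 − (1 − q)^k.

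| q (assumed) | k = 5 | k = 6 |
|---|---|---|
| 1% | 4.9% | 5.9% |
| 2% | 9.6% | 11.4% |
| 3% | 14.1% | 16.7% |
| 5% | 22.6% | 26.5% |
| 8% | 34.1% | 39.4% |
| 10% | 41.0% | 46.9% |

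At q = 5%, about 107 (k = 5) or 101 (k = 6) of 138 participants remain, or 155 or 147 of the maximum of 200 (Protocol section 6, Part 2).

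**3. Literal rule, misses clustered within people.** With a beta-binomial model, mean q = 5% and within-person correlation ρ, take a = q(1 − ρ)/ρ and b = (1 − q)(1 − ρ)/ρ. The share excluded is 1 − B(a, b + k)/B(a, b).

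| ρ (assumed) | k = 5 | k = 6 |
|---|---|---|
| 0.1 | 19.1% | 21.7% |
| 0.3 | 14.4% | 15.7% |
| 0.5 | 11.0% | 11.7% |

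**4. Literal rule, using the plan's 20% loss allowance.** That allowance was set for the 12-month primary outcome; applying it to MHQ is an assumption. With a rate r of intermittent misses among the remaining participants, the share excluded is 1 − 0.8(1 − r)^k:

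- r = 0: 20.0%
- r = 1%: 23.9% (k = 5) or 24.7% (k = 6)
- r = 2%: 27.7% or 29.1%

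**5. Visit-level rule.** At an independent q = 5%, about 5% of forms are lost. Almost nobody loses all five follow-ups: 0.05⁵ = 3 × 10⁻⁷. However, baseline is a covariate, so unless a rule is stated, a follow-up score is usable only if baseline is also present. The share of follow-up scores lost is then 1 − (1 − q)²: 5.9%, 9.8% and 19.0% at q = 3%, 5% and 10%. This is the fair comparison with step 2, and it shows why the fix must cover baseline.

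**6. Precision.** If precision scales with the number of participants, excluding a fraction x multiplies the standard error by 1/√(1 − x). For x = 5% this is 1.03; for x = 25% it is 1.15.

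**The case against.** The strongest reply is that nobody meant the sentence literally. Read with the sentence that follows, it can mean that a wholly missing form yields no score at that visit while a partial form is scored by Appendix 3. Several places support this:

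- SAP 6.3 and 4.2 both work from available data.
- The MHQ summary and model shells in SAP Appendix 5 have a separate n at each time-point, whereas a completers set would give one constant n.
- SAP 15.1 (iv) adds second 12- and 18-month questionnaires as an extra time-point. Only participants with delayed assessments have these, so a rule demanding a form at every time-point could not operate there.

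This stands as evidence of intent, so a reader should not conclude that the SAP has definitely adopted a completers analysis. It does not remove the need to act, because the sentence still states the participant as the unit.

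A reader might also infer that about a quarter of the sample would be lost. The documents do not support a single figure. A quarter requires an independent miss rate of about 5% per visit, or the 20% loss allowance plus 1% to 2% intermittent misses. Clustering lowers it, and sending forms by email or post (Protocol 8.6 and 8.8; SAP Appendix 6) should reduce misses.

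A third tempting inference concerns injection experience. If the nodule has shrunk too far for accurate delivery, "then the clinician may decide to not inject on that visit" (Protocol section 6, Part 2), and one might think such participants drop out of that analysis. SAP 6.1 measures injection experience after each injection, so when none is given no form is due and none is incomplete.

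Finally, SAP 4.1 treats secondary outcomes as supportive only. That limits the consequence but does not excuse the inconsistency.

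**Conclusion.** The point holds as an internal conflict. The literal wording of SAP 6.3.1 excludes participants, while SAP 6.3 and 4.2 keep them with whatever data they have. Visit-level handling was probably intended. If the sentence were followed as written, it would discard usable visits and select on attendance in a key secondary outcome.

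The size cannot be derived from the documents. Under independent misses at 1% to 10% per visit over five or six questionnaires, exclusion runs from about 5% to 47%. At a 5% rate with within-person correlation of 0.1 to 0.5, it is about 11% to 22%. All these rates are assumptions. Neither the primary analysis of nodule hardness nor the sample size of 138 is affected. The wording should be corrected, but the trial's main conclusion does not depend on it.

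**What to change.** Replace the sentence in SAP 6.3.1 with: *A wholly missing questionnaire is treated as missing at that time-point only; the participant's other available scores stay in the mixed model; partially completed questionnaires are scored by Appendix 3.*

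Add one sentence on how a missing baseline score is handled. Without it, a missing baseline form would still remove all of that participant's follow-up scores, even under a visit-level rule.

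Optionally, note that for injection experience a visit without an injection has no questionnaire due. This is only a clarification.

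The cost is a short SAP edit, with no new data and no change to the sample size or primary analysis. It can be settled at the blinded analysis that SAP 3.6 already places before data lock.
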